2. TRIAL DESIGN

2.1 Trial summary and flow diagram

This will be a single blinded, multi-centre, randomised placebo controlled trial. The considered opinion of the Arthritis Research UK CSG Think Tank – which included representatives from rheumatology, podiatry, orthopaedics, physiotherapy, general practice and research – was that in the non-athletic population there is very limited evidence of the effectiveness of eccentric loading exercises, or indeed any other intervention, for this condition. It was the considered opinion of the Think Tank that there was no ‘standard treatment’ for the general population. Therefore, the

pivotal and crucial trial design which is likely to influence clinical practice should involve a placebo-arm.

[figure not shown]
All patients who are willing to proceed will be approached by a suitably qualified member of the research team who are responsible for completing consent procedures and baseline demographic data and functional outcomes using VISA-A and EQ-5D-5L **before randomisation**. The patient will be randomised using a centralised telephone randomisation service to either the intervention or the placebo injection, on a 1:1 basis, stratified by centre and presence of bilateral symptoms. **After randomisation**, the suitably qualified member of the research team will then prepare the allocated injection for the principal investigator who will administer the injection. The participant will not know the treatment allocation.

Two hundred and forty patients will be randomised in total, across six participating centres. The intervention delivery will be standardised through initial training and on-going quality assurance checks by an independent researcher. The participants will then attend routine clinical appointments, (typically two weeks post injection to assess for any adverse events and six months post injection to review treatment efficacy). The participants will also receive two postal follow up questionnaires, as part of research procedures, at three and six months following randomisation.

The local principal investigator and research team at each site cannot be blind to treatment as they will be delivering the interventions. None of these team members will have a role in the collection of participant data after randomisation or analysis, beyond reporting adverse events.

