2.2.2 Secondary objective

Secondary Objectives:

1) To quantify and draw inferences on observed differences in VISA-A status at three months after treatment.

2) To identify any differences in health related quality of life measurement between trial treatment groups at three and six months after treatment.

3) To determine the complication rate of platelet rich plasma injections at three and six months after treatment.

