There is an active debate pertaining to the treatment effect of needling trauma, or the trauma of injecting fluid directly into the tendon. Therefore, a true placebo arm would need to avoid these possible treatment effects. The group consensus was therefore not to administer the placebo injection intratendinously.

Post Injection:

The participant will not be aware which treatment they have received, but the PI administering the treatment will.

After both treatments all participants will receive the same post injection advice sheet. The post injection advice sheet will inform participants that they may have increased pain for 24-48 hours, after which period they can resume their normal activities as pain allows. It will also include advice on potential adverse events (e.g. infection and reddening of the skin) and what to do if they occur.

In the case of participants with bilateral presentations, the index tendon will be randomised and managed accordingly. Regarding the non-index tendon the participant will have two options, to have no treatment or to receive a second injection into the non-index tendon.

All participants will then be followed up at standard clinical follow up appointments. These usually occur on two further occasions at two weeks after the injection and six months. The appointment at two weeks will allow the PI to check for the occurrence of any early complications (e.g. infection). The appointment at six months will allow the PI to assess the outcome from a clinical perspective and discuss with the participant at this point if any further clinical management is required.

Research follow up will be by postal questionnaire and will take place at three and six months after randomisation.

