The stratified randomisation procedure will ensure a balance in recruiting centres between test treatments. In addition to the unadjusted analysis (t-tests) we will also undertake regression analyses to adjust for any imbalance between test treatment groups in patient age or gender. The fixed effects analysis (linear regression model) will also be generalized by adding a random effect for recruiting centre to allow for possible heterogeneity in patient outcomes due more generally to the recruiting centre. VISA-A data will be assumed to be normally distributed during modelling, but subsidiary analyses may also be undertaken after appropriate variance-stabilizing transformation. The primary focus will be the comparison of the two treatment groups of patients, and this will be reflected in the analysis which will be reported together with appropriate diagnostic plots that check the underlying model assumptions. Treatment effects will be presented, with appropriate 95% confidence intervals, for both the unadjusted and adjusted analyses.

Temporal patterns of any complications will be presented graphically and if appropriate a time-to-event analysis (Kaplan-Meier survival analysis) will be used to assess the overall risk and risk within individual classes of important complications (e.g. infection). The decision about whether to undertake a time-to-event analysis will be data dependent; that is it will be dependent on the number of complications reported by study participants. The independent Data Monitoring and Ethics Committee will advise on this and suggest appropriate modifications to the statistical analysis plan as data is accumulated.

From the pilot data two patients from a sample of twenty presented with bilateral Achilles tendinopathy. For the full trial this small group will be randomised and treated as one unit i.e. the patient will be randomised rather than the tendon. Therefore, study participants presenting with bilateral tendinopathy will receive the same treatment on both sides. One side will be randomly selected, and designated as the index Achilles tendon. For those outcome measures (complications) that are side specific, we will use data from the index side only in the analysis. Randomisation will ensure approximate balance in bilaterals between groups; however, bilaterality will also be adjusted for in the definitive analysis. This will be incorporated into the Statistical Analysis Plan.

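### Side-specific complications are analysed on the index tendon only, so local harms of a second trial injection in bilateral participants are recorded but left out of the group complication analysis

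*Protocol*

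**What the plan says.** Section 6.2 of the protocol sets the rule: "For those outcome measures (complications) that are side specific, we will use data from the index side only in the analysis". The parenthesis names complications, so this is a rule about harms.

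Secondary objective 3 in section 2.2.2 is wider: "To determine the complication rate of platelet rich plasma injections at three and six months after treatment". It mentions no index side.

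On treatment of the second tendon, section 2.6.3 says: "Regarding the non-index tendon the participant will have two options, to have no treatment or to receive a second injection into the non-index tendon". It does not name the content of that second injection. Section 6.2 says that "study participants presenting with bilateral tendinopathy will receive the same treatment on both sides". On the unit, section 6.2 says that "the patient will be randomised rather than the tendon".

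Adverse event collection (sections 2.3.2 and 4.1.1) is not restricted by side. Section 4.1.1 lists infection, bleeding at the injection site, swelling and skin discolouration among the expected events, to be recorded on the CRF without 24-hour reporting. Section 6.2 gives infection as its example of an important complication for a possible Kaplan-Meier analysis. The protocol describes no table or analysis of non-index complications.

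**The concern.** Limiting side-specific data to one tendon per patient is a usual way to avoid double counting in efficacy. For harms it has a cost. A second injection given under the protocol can cause a local infection or bleed on that side, and section 6.2 keeps that event out of the comparison between arms. Someone whose only complication is on the non-index side then contributes no event to the complication analysis, although the patient is the randomised unit and received the injection in the trial.

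The PRP procedure injects about 3 ml with five penetrations of the tendon. The placebo needle goes under the skin and nothing is injected (section 2.6.3). If PRP carries more local harm, more events are lost from the PRP arm in absolute terms. At stake is whether the trial's answer to its safety objective reflects all the injections it gave.

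**Working it through.** The protocol states no complication rate, so there is no figure of its own to reproduce here. The check compares what the rule counts with what the trial delivers.

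**Inputs from the protocol**
- 240 randomised 1:1 (section 2.1), so 120 per arm.
- Bilateral share from the pilot (section 6.2): 2/20 = 10%. The exact (Clopper-Pearson) 95% interval is 1.2% to 31.7%.

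**Assumptions, because the protocol gives no figures**
- Uptake of the second injection: 0%, 50% or 100%.
- Second-side injection is PRP in the PRP arm, as section 6.2 implies.
- Risk of a side-specific complication: 5% per injection, independent between sides, unless stated otherwise.

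**1. PRP injections outside the analysis.** Second injections s = 120 × bilateral share × uptake; unused share = s/(120 + s).

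| Bilateral share | Uptake | s | Unused share |
|---|---|---|---|
| 10% | 0% | 0 | 0% |
| 10% | 50% | 6 | 6/126 = 4.8% |
| 10% | 100% | 12 | 12/132 = 9.1% |
| 1.2% | 100% | 1.5 | 1.5/121.5 = 1.2% |
| 31.7% | 100% | 38 | 38/158 = 24% |

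**2. Rate per injection.** With 10% bilateral and full uptake, the index side alone gives 120 × 0.05 = 6.0 expected events, and 6.0/120 = 5.0%. All injections give 132 × 0.05 = 6.6 events, and 6.6/132 = 5.0%. The rates are equal. At constant risk the rule costs information and does not bias this rate.

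**3. Risk per participant.** With bilateral share p, full uptake and risk r per injection, the any-side risk is (1 − p)r + p[1 − (1 − r)²].
- p = 10%, r = 5%: 0.9 × 0.05 + 0.1 × 0.0975 = 0.0548, or about 5.5%. The rule counts 5.0%.
- p = 31.7%, r = 5%: 0.683 × 0.05 + 0.317 × 0.0975 = 6.5%, against 5.0%.
- Bilateral participants alone, r = 5%: 9.75%, against 5.0%.

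**4. Comparison between arms.** Take assumed risks of 5% (PRP) and 1% (placebo), 10% bilateral and full uptake in both arms. The any-side placebo risk is 0.9 × 0.01 + 0.1 × 0.0199 = 1.10%.
- Difference: 5.0 − 1.0 = 4.0 points on the index side; 5.48 − 1.10 = 4.4 points on any side.
- Ratio: 5.0 on the index side; 5.48/1.10 = 4.98 on any side.

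The difference shrinks under the index-side rule and the ratio is practically unchanged.

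**The case against.** A reader might infer that the rule biases the PRP complication rate downward. Objective 3 is worded as a rate of injections, and step 2 shows that an index-only numerator over index tendons gives the same rate as all injections over all treated tendons when risk is constant. That inference is not supported.

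A reader might also infer that these harms vanish from the trial's safety information. They do not. All adverse events go on the CRF whatever the side, serious events have their own form, participants are asked about adverse events at each questionnaire, and the DMC reviews safety data. Systemic and venesection events are not side specific and stay in the analysis. Nor is the comparison distorted in relative terms: the rule is the same in both arms, and bilaterality is a stratification factor.

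Two further points have weight. The 9% and 24% figures are ceilings at full uptake. Counting any injected side also makes exposure depend on a choice that section 2.6.3 leaves to the participant, whereas one index tendon per patient gives equal exposure, so the index-side figure is a defensible summary.

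What remains is narrower. The risk per participant is understated, and the protocol describes no other place where second-side complications are compared by arm. This is not detail left to the statistical analysis plan: the protocol fixes the rule itself.

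**Conclusion.** The point holds as a limited one about the group complication analysis. Up to 9% of PRP injections at the pilot's bilateral share contribute nothing on side-specific complications: none if nobody takes a second injection, and about 1% to 24% over the pilot's interval if everyone does. The risk per participant is understated by about half a percentage point at an assumed 5% risk per injection, independent sides, 10% bilateral and full uptake. Under the same conditions and an assumed 1% placebo risk, the absolute difference between arms is 4.0 instead of 4.4 points.

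The documents do not support a claim that the per-injection rate is biased, that the harms go unrecorded, or that the relative comparison is materially changed. The effect is probably modest overall and concentrated in bilateral participants. A change is worthwhile because it is cheap and the safety objective is not limited to one side.

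The number of affected injections also cannot be settled while the protocol contradicts itself. The second injection is optional in section 2.6.3, but section 6.2 has both sides receiving the same treatment. The index tendon is the one perceived as more severe in section 2.4.2 and is randomly selected in section 6.2.

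**What to change.** - **Safety analysis.** Count each participant once if a complication occurs on any side injected in the trial, or systemically. This respects the randomised unit and avoids double counting.
- **Alongside it.** Show the rate per injected tendon and the index-side rate. The first deals with the drawback that exposure now depends partly on the option of a second injection; the second keeps the equal-exposure comparison.
- **Scope of the index-side rule.** Keep it where side matters for efficacy, and state that it does not define the main safety result.
- **Data.** Record the side of each local event on the adverse event form, if the form does not already do so, and record whether the second tendon was injected.
- **Reconcile.** Bring sections 2.6.3 and 6.2 into agreement on treatment of the non-index tendon, and sections 2.4.2 and 6.2 on how the index tendon is chosen.

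The cost is a sentence or two of analysis wording, a small check of the form and the two corrections of text. The sample size and the primary analysis are unaffected.

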7. TRIAL ORGANISATION AND OVERSIGHT

7.1 Sponsor and governance arrangements

University of Warwick will act as sponsor for the trial, using WCTU's SOPs.

7.2 Regulatory authorities/ethical approval

All required ethical approval(s) for the trial will be sought using the Integrated Research Application System.

Before enrolling patients into the trial, each trial site will ensure that the local conduct of the trial has the approval of the relevant NHS Trust Research & Development (R&D) department. Sites will not be permitted to enrol patients into the trial until written confirmation of R&D approval is received by WCTU.

7.3 Trial Registration

The study will be registered with the International Standard Randomised Controlled Trial Number (ISRCTN) Register.

7.4 Indemnity

NHS indemnity covers NHS staff, medical academic staff with honorary contracts, and those conducting the trial. NHS bodies carry this risk themselves or spread it through the Clinical Negligence Scheme for Trusts, which provides unlimited cover for this risk. The University of Warwick provides indemnity for any harm caused to participants by the design of the research protocol.

7.5 Trial timetable and milestones

Months	Years		Centre 1	Centre 2	Centre 3	Centre 4	Centre 5	Centre 6	Total	Notes
0	1	01/09/2015	ethics approval, ISRCTN registration Contracting & R&D centres 1-6							
1		01/10/2015	Finalise protocol, CRF's & training materials							
2		01/11/2015								
3		01/12/2015	Finalise DMC, TMG and TSC membership and WMS appointments							
4		01/01/2016	Purchase equipment							
5		01/02/2016								
6		01/03/2016	Training centres 1&2							
7		01/04/2016	Training centres 3&4							
8		01/05/2016	Training centres 5&6							
9		01/06/2016	1.4	1.4					2.8	Recruitment 1&2
10		01/07/2016	1.4	1.4					5.6	
11		01/08/2016	1.4	1.4					8.4	
12	2	01/09/2016	1.4	1.4	1.4	1.4			14	Recruitment 3&4
13		01/10/2016	1.4	1.4	1.4	1.4			19.6	
14		01/11/2016	1.4	1.4	1.4	1.4			25.2	
15		01/12/2016	1.4	1.4	1.4	1.4	1.4	1.4	33.6	Recruitment 5&6
16		01/01/2017	1.4	1.4	1.4	1.4	1.4	1.4	42	
17		01/02/2017	1.4	1.4	1.4	1.4	1.4	1.4	50.4	
18		01/03/2017	1.4	1.4	1.4	1.4	1.4	1.4	58.8	
19		01/04/2017	1.4	1.4	1.4	1.4	1.4	1.4	67.2	
20		01/05/2017	1.4	1.4	1.4	1.4	1.4	1.4	75.6	
21		01/06/2017	1.4	1.4	1.4	1.4	1.4	1.4	84	
22		01/07/2017	1.4	1.4	1.4	1.4	1.4	1.4	92.4	
23		01/08/2017	1.4	1.4	1.4	1.4	1.4	1.4	100.8	
24	3	01/09/2017	1.4	1.4	1.4	1.4	1.4	1.4	109.2	
25		01/10/2017	1.4	1.4	1.4	1.4	1.4	1.4	117.6	
26		01/11/2017	1.4	1.4	1.4	1.4	1.4	1.4	126	50% recruitment
27		01/12/2017	1.4	1.4	1.4	1.4	1.4	1.4	134.4	
28		01/01/2018	1.4	1.4	1.4	1.4	1.4	1.4	142.8	
29		01/02/2018	1.4	1.4	1.4	1.4	1.4	1.4	151.2	
30		01/03/2018	1.4	1.4	1.4	1.4	1.4	1.4	159.6	
31		01/04/2018	1.4	1.4	1.4	1.4	1.4	1.4	168	
32		01/05/2018	1.4	1.4	1.4	1.4	1.4	1.4	176.4	
33		01/06/2018	1.4	1.4	1.4	1.4	1.4	1.4	184.8	
34		01/07/2018	1.4	1.4	1.4	1.4	1.4	1.4	193.2	
35		01/08/2018	1.4	1.4	1.4	1.4	1.4	1.4	201.6	
36	4	01/09/2018	1.4	1.4	1.4	1.4	1.4	1.4	210	
37		01/10/2018	1.4	1.4	1.4	1.4	1.4	1.4	218.4	
38		01/11/2018	1.4	1.4	1.4	1.4	1.4	1.4	226.8	
39		01/12/2018	1.4	1.4	1.4	1.4	1.4	1.4	235.2	
40		01/01/2019	1.4	1.4	1.4	1.4	1.4	1.4	243.6	Total recruitment
41		01/02/2019	Final follow up							
42		01/03/2019								
43		01/04/2019								
44		01/05/2019								
45		01/06/2019								
46		01/07/2019								
47		01/08/2019	Data review and statistical analysis							
48	5	01/09/2019	Close sites							
49		01/10/2019								
50		01/11/2019	Final report and dissemination							
51		01/12/2019								
52		01/01/2020								

7.6 Administration

The trial co-ordination will be based at WCTU, University of Warwick.

7.7 Trial Management Group (TMG)

The Trial Management Group, consisting of the project staff and co-investigators involved in the day-to-day running of the trial, will meet regularly throughout the project. Significant issues arising from management meetings will be referred to the Trial Steering Committee or Investigators, as appropriate.

7.8 Trial Steering Committee (TSC)

The trial will be guided by a group of respected and experienced personnel and trialists as well as at least one 'lay' representative. The TSC will have an independent Chairperson. Face to face meetings will be held at regular intervals determined by need but not less than once a year. Routine business is conducted by email, post or teleconferencing.

The Steering Committee, in the development of this protocol and throughout the trial will take responsibility for:

- Major decisions such as a need to change the protocol for any reason
- Monitoring and supervising the progress of the trial
- Reviewing relevant information from other sources
- Considering recommendations from the DMC
- Informing and advising on all aspects of the trial

7.9 Data Monitoring Committee (DMC)

The DMC will consist of independent experts with relevant clinical research, and statistical experience. The DMC will meet after the first 50% of patients have been recruited and regularly thereafter. Confidential reports containing recruitment, protocol compliance, safety data and interim assessments of outcomes will be reviewed by the DMC. The DMC will advise the TSC as to whether there is evidence or reason why the trial should be amended or terminated.

The Data Monitoring Committee (DMC) will be established in line with the charter set by WCTU. The Data Monitoring Committee (DMC) will be independently chaired and established in accordance with the principles of Good Clinical Practice, WCTU Standard Operating Procedures (SOPs) and Arthritis Research UK Oversight Committee guidance.

(1) There will be no a priori stopping rules set for efficacy. Experience suggests that the nature of trial design is such that there is unlikely to be sufficient data available to make decisions regarding efficacy prior to the end of the recruitment phase of the study. This will in part be determined by the study recruitment patterns, which will be routinely monitored by DMC, therefore they may decide that a narrow window of opportunity does exist to assess treatment efficacy. If so, they are at liberty under the DMC charter to make recommendations and suggestions to the Trial Management and Steering Committees at end stage of the study.

(2) The study statistical analysis plan, which will be agreed with all parties at the commencement of the trial. The DMC will feedback their recommendation, on whether in their view the trial should proceed, to the TSC who will meet immediately after this time-point. The DMC

will make a recommendation only to the TSC, but ultimately it will be the responsibility of the independently chaired TSC to decide on whether the trial will proceed to the planned sample size, or be curtailed early.

(3) Regarding stopping rules for safety, these will be discussed and agreed by the independent committee prior to the commencement of recruitment and reviewed annually thereafter, or more frequently if deemed necessary.

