6. STATISTICAL ANALYSIS

6.1 Power and sample size

There is no consensus on a minimum clinically important difference (MCID) regarding the VISA-A score. However, previous studies propose that the MCID lies between 10 and 12 points and that this is in keeping with comparable patient reported outcomes in musculoskeletal medicine. We have therefore chosen an MCID of 12 points.

From our pilot data, the VISA-A data were observed to be approximately normally distributed with a standard deviation of 26. If the true difference between the experimental and control treatment group means is 12, a sample of 100 patients in each group will be required to reject the null hypothesis (population means of the experimental and control groups are equal) with probability 0.9 (90% power). This equates to an effect size of 0.46 (12/26), which we would consider to be moderate. The Type I error rate (significance level) associated with this test is 5%. Allowing approximately 20% loss to follow-up, this amounts to 240 patients in total

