6.2 Statistical Analysis Plan

It seems likely that some data may not be available due to voluntary withdrawal of participants, lack of completion of individual data items or general loss to follow-up. Where possible the reasons for data 'missingness' will be ascertained and reported. Although missing data is not expected to be a problem for this study, the nature and pattern of the missingness will be carefully considered, including in particular whether data can be treated as missing completely at random or missing at random. If judged appropriate, missing data will be imputed using the multiple imputation facilities (mice package) available in R (<http://www.r-project.org/>). The resulting imputed datasets will be analysed and reported, together with appropriate sensitivity analyses. Any imputation methods used for scores and other derived variables will be carefully considered and justified. Reasons for ineligibility, non-compliance, withdrawal or other protocol violations will be stated and any patterns summarized. More formal analysis, for example using logistic regression with 'protocol violation' as a response, may also be appropriate and aid interpretation.

Standard statistical summaries (e.g. medians and ranges or means and variances, dependent on the assumed distribution of the outcome) and graphical plots showing correlations will be presented for the primary outcome measure and all secondary outcome measures. Baseline data will be summarised to check comparability between treatment arms, and to highlight any characteristic differences between those individuals in the study, those ineligible, and those eligible but withholding consent.

The main analysis will investigate differences in the primary outcome measure, the VISA A at six months after treatment, between the two treatment groups on an intention-to-treat basis. In addition, early functional status will also be assessed and reported at three months. The differences between treatment groups will be assessed using a Student t-test, based on a normal approximation for the VISA A score at 6 months, and at other occasions. Tests will be two-sided and considered to provide evidence for a significant difference if p-values are less than 0.05 (5% significance level). Estimates of treatment effects will be presented with 95% confidence intervals.

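### Section 7.9 rules out any pre-set efficacy stopping rule yet leaves an efficacy assessment open, so the stated 5% type I error is not protected if that discretion is used

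*Protocol*

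**What the plan says.** **Interim outcome data.** Under section 7.9 the DMC first meets once half the patients are recruited, and at regular intervals after that. Among the contents of its confidential reports, "safety data and interim assessments of outcomes will be reviewed by the DMC".

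**Efficacy.** Section 7.9(1) opens: "There will be no a priori stopping rules set for efficacy". It explains that enough data for an efficacy decision are unlikely before recruitment ends. It then adds that, depending on recruitment, "they may decide that a narrow window of opportunity does exist to assess treatment efficacy", and that the DMC may in that case make recommendations towards the end of the study.

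**Early ending.** Section 7.9(2) has the DMC advise on whether the trial should go on. The TSC decides whether to run to the planned size or stop short.

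**Interim analyses.** Section 6.2 allows these only at the DMC's direction. It gives no number, timing or threshold.

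**Final test.** Section 6.1 sets the type I error at 5%. Under section 6.2 the two-sided tests are "considered to provide evidence for a significant difference if p-values are less than 0.05". Neither section mentions an allowance for earlier looks.

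**Changes to the analysis plan.** The paragraph of section 6.2 on complications ends: "The independent Data Monitoring and Ethics Committee will advise on this and suggest appropriate modifications to the statistical analysis plan as data is accumulated".

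**The concern.** A single test at 5% has a 5% false-positive rate only if it is the sole occasion on which efficacy can be declared. Section 7.9(1) opens a possible second occasion and also says that no rule for it will be set in advance. This is more than detail left to the analysis plan or the DMC charter, because a boundary placed there would contradict the protocol's own statement. Safety is handled differently: section 7.9(3) requires its stopping rules to be agreed before recruitment starts.

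The primary inference is at stake. If the trial ended on a favourable look with no boundary, the p-value and 95% confidence interval for VISA-A would not have their nominal properties. That could not be fully repaired afterwards, because the rule that led to the stop would never have been defined.

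**Working it through.** **The plan's own figure.** Inputs from section 6.1: difference 12, SD 26, two-sided 5%, power 90%. Per group, n = 2 × (1.960 + 1.282)² × 26² / 12² = 98.7, so 99. The stated 100 per group gives 90.1% power by the noncentral t. The sample size therefore reproduces as a fixed design with one final test.

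**Information at possible looks.** The section 7.5 recruitment table is lagged by six months, because the primary outcome is at six months. Equal loss over time is assumed.

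| Look | Recruited | With six months elapsed | Information fraction |
|---|---|---|---|
| Month 26 (50% recruitment in the table) | 126 | 75.6 (month 20 total) | 75.6/240 = 0.315 |
| Month 38 (illustrative later meeting) | 226.8 | 176.4 (month 32 total) | 176.4/240 = 0.735 |
| Month 40 (end of recruitment) | 243.6 | 193.2 (month 34 total) | 193.2/243.6 = 0.79; 193.2/240 = 0.805 |

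**Overall type I error.** Under the null hypothesis the test statistics at information fractions t₁ < t₂ < … are jointly normal with correlation √(tᵢ/tⱼ). The overall error is 1 − P(|Zᵢ| < cᵢ at every look). With one interim look at 0.79 the correlation with the final statistic is √0.79 = 0.889; at 0.315 it is √0.315 = 0.561.

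| Interim look(s), then the final test at 0.05 | Interim judged at p<0.05 | Interim judged at p<0.001 |
|---|---|---|
| One at 0.79 to 0.805 | 7.1% | 5.0% |
| One at 0.50 | 8.3% | 5.0% |
| One at 0.315 | 8.9% | 5.0% |
| Two, at 0.315 and 0.735 | 10.7% | 5.1% |

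The interim threshold matters as much as the timing. One look at 0.79 judged at p<0.01, with the final test at 0.05, gives 5.1%. If no look can stop the trial for efficacy or alter the VISA-A analysis, the error is 5% however often the DMC sees the data.

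**The case against.** The case for leaving the text alone has five parts.

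1. *The protocol describes a late and exceptional event, not a licence to stop from 50% recruitment.* This stands. A reader might take the 50% meeting as an efficacy stopping point, but section 7.9(1) calls efficacy decisions before the end of recruitment unlikely and places recommendations near the end of the study. The single late look (about 7.1%) is therefore the figure closest to the text, and 8.9% and 10.7% show what the open wording could reach. By month 40 there is no recruitment left to cut. Even so, about 20% of participants (1 − 193.2/243.6 = 0.21) would not yet have reached six months, so an efficacy conclusion before full data remains possible.

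2. *Seeing outcomes does not inflate the error, and the protocol does not say that the interim assessments compare the arms.* Both are correct. The exposure comes from the permission to assess efficacy with no rule, not from the reports.

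3. *No threshold of 0.05 is stated for a look.* Correct. A cautious DMC could keep the error close to 5%, but nothing in the protocol requires it to.

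4. *The early-ending text in 7.9(2) is general.* It is, and it serves safety and feasibility too. It does not exclude efficacy.

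5. *The sentence on analysis-plan changes concerns complications.* Largely right. It follows directly from the choice of a time-to-event analysis of complications. A reader might infer that the DMC is invited to reshape the VISA-A test after seeing results, but the context does not support that. Section 6.2 also has the plan agreed at the start and amendments stated and justified. What remains is that the sentence's wording carries no explicit limit.

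**Conclusion.** The point holds as a conditional one. The protocol claims a 5% type I error, declines to set an efficacy rule, and leaves an efficacy assessment and an early end open. The 5% is therefore not protected if the discretion is exercised. It would go too far to say that the error is inflated: that would need a look able to lead to an efficacy stop, and the protocol does not plan one.

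The size is about 7.1% for the late look the text points to, 8.9% for one look at the 50%-recruitment meeting, and 10.7% for looks at 0.315 and 0.735. All three assume p<0.05 at each look, equal loss over time and recruitment as in section 7.5. The protocol fixes neither the number of looks nor their threshold, and the second date in the two-look case is illustrative. The analysis-plan sentence in section 6.2 is a minor wording point, and the conclusion does not depend on it.

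**What to change.** **Section 7.9(1).** Replace the text on a possible efficacy window with one of two statements:

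- no interim look may lead to stopping for efficacy; or
- any comparative look at VISA-A uses a strict boundary fixed in advance, such as Haybittle-Peto (two-sided p<0.001), with the final test at 0.05.

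The first keeps the error at 5%; the second gives 5.0% to 5.1% for the schedules above. The DMC charter and the analysis plan should carry the same wording. Safety stopping under 7.9(3) is not affected.

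**Section 6.2 (minor).** Limit the DMC's advice on analysis-plan changes to the time-to-event analysis of complications, with that choice based on the pooled number of complications. State that changes to the VISA-A analysis come only from people without access to comparative data. There is no need to delete the DMC's advisory role.

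**Cost.** Wording in three documents and no change to the planned sample size. The real downside is that the DMC gives up the freedom to stop on moderate interim evidence of benefit.
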